2.6.4 Supportive analyses

To complement the secondary estimand analysis of average changes in hemoglobin under a hypothetical strategy, the analysis evaluating average changes in hemoglobin will be repeated using a treatment policy approach, to obtain the estimation of the combination of Iptacopan+transfusions as needed.

Supportive analyses on the secondary endpoints: change from baseline in LDH, FACIT, reticulocytes will be performed under a hypothetical strategy. For these analyses, the values on these 3 endpoints in the 30 days following transfusion will be considered missing and the values will be imputed. The imputation methods will be similar to those outlined in [Section 2.6.2](#).

2.7 Safety analyses

Unless otherwise specified all safety summaries will be presented by SAF. Safety summaries based on only core treatment period and overall (based on information from core treatment period and extension treatment period) will be produced as appropriate.

Safety summaries (tables, figures) include only data from the on-treatment period with the exception of baseline data which will also be summarized where appropriate (e.g., change from baseline summaries). In particular, summary tables for adverse events (AEs) will summarize only on-treatment events, with a start date during the on-treatment period (treatment-emergent AEs). In addition, a separate summary of death events including on treatment and post treatment deaths will be provided if appropriate.

The on-treatment period lasts from the date of first administration of study treatment to 7 days after the date of the last actual administration (including core treatment period, extension treatment period and tapering procedures after permanent treatment discontinuation) of iptacopan which covers slightly more than 5 times the estimated half-life of iptacopan.

2.7.1 Adverse events (AEs)

All information obtained on AEs will be displayed by participant.

The number (and percentage) of participants with treatment emergent AEs (events starting after the first dose of study medication or events present prior to start of treatment but increased in

severity based on preferred term) and treatment emergent serious adverse events (SAEs) will be summarized in the following ways:

- by primary system organ class (SOC) and preferred term (PT).
- by primary SOC, PT and maximum severity.

Separate summaries will be provided for study treatment emergent AEs, death, SAEs, and AEs leading to discontinuation of study medication, and for iptacopan tapering if this is followed prior to complete study dose discontinuation. For patients receiving iptacopan, treatment emergent SAEs and AEs with PTs in the AESI 'PNH haemolysis and thrombosis' occurring after discontinuation of iptacopan 200 mg b.i.d will be reported separately.

A participant with multiple AEs within a primary SOC is only counted once towards the total of the primary SOC.

Most frequent AEs, most frequent SAEs, AEs leading to treatment discontinuation will be presented by preferred term.

Summaries presenting exposure adjusted incidence rates and associated 95% CI based on TEAEs and treatment emergent SAEs will be provided. AEs (including pre-treatment, on-treatment, post-treatment events) will be listed.

In order to address the issue of variable follow-up duration within study, the exposure adjusted incidence rate of TEAE will be presented by primary SOC and PT.

For the most common AEs, the 95% CI of the exposure adjusted incidence rate of TEAE can be presented.

Exposure adjusted incidence rate and 95% confidence interval

For summary tables on exposure-adjusted AEs, the number of episodes per 100 patient years will be presented. The occurrence rate (number of episodes per 100 patient years) will be calculated as $100 \times (\text{the total number of AE episodes from all patients in the population} / \text{the total number of patient-years})$. A patient may have multiple occurrences of the same event. All occurrences are counted. Total patient years will be computed as (sum of the duration of on-treatment periods over patients, in days)/365.25. The approximately 95% CIs for the occurrence rate will be calculated with correction for overdispersion using the asymptotically robust method ([Scosyrev 2016](#), [Scosyrev and Pethe 2022](#)).

This method will account for the length of follow-up time under the assumption that events would occur with the same frequency at any point in time. Although this analysis is referred to as "Exposure adjusted" it actually uses by default the on-treatment ([Section 2.7](#)) which includes periods of interruption during which there is no exposure.

2.7.1.1 Adverse events of special interest / grouping of AEs

Adverse events of special interest (AESI) are defined in the latest version of the compound electronic Case Retrieval Strategy (eCRS) that is stored in the Global Programming System (GPS). This classification reflects the safety topics of interest identified in the current version of the iptacopan Development Safety Profiling Plan, and may be updated based on review of accumulating data. At the time of analyses, the latest version of the eCRS will be used to identify the AESIs. Safety topics of interest to be reported are identified by the flag "SP".

The number (and percentage) of participants with treatment-emergent adverse events of special interest/related to identified and potential risks will be summarized. The frequency and percentage of participants with treatment emergent adverse events of special interest (TEAESI) and serious TEAESI will be summarized by preferred team. The exposure adjusted incidence rates and associated 95% CI (as stated in [Section 2.7.1](#)) will be presented for each safety topic of interest AEs/SAEs.

A listing of participants experiencing AESIs will also be provided. The eCRS safety topic definitions to identify AESIs will be provided as a listing.

For patients receiving iptacopan, treatment-emergent and all AESI within the search 'PNH haemolysis and thrombosis' occurring after discontinuation of iptacopan 200 mg b.i.d will be reported. All such AEs occurring after iptacopan 200 mg b.i.d will be listed and the TEAEs will be flagged.

2.7.1.2 Adverse events reporting for safety disclosure

For the legal requirements of clinicaltrials.gov and EudraCT, two required tables on TEAEs which are not SAEs with an incidence greater than a certain threshold and on TESAEs and SAE suspected to be related to study treatment, will be provided by SOC and PT on the safety set population. If for a same patient, several consecutive AEs (irrespective of study treatment causality, seriousness and severity) occurred with the same SOC and PT:

- a single occurrence will be counted if there is ≤ 1 day gap between the end date of the preceding AE and the start date of the consecutive AE
- more than one occurrence will be counted if there is > 1 day gap between the end date of the preceding AE and the start date of the consecutive AE.

For occurrence, the presence of at least one SAE / SAE suspected to be related to study treatment / non SAE has to be checked in a block e.g., among AE's in a ≤ 1 day gap block, if at least one SAE is occurring, then one occurrence is calculated for that SAE.

The number of deaths resulting from SAEs suspected to be related to study treatment and SAEs irrespective of study treatment relationship will be provided by SOC and PT.

2.7.2 Deaths

The number of deaths resulting from TEAEs will be summarized by SOC and PT. Death refers to TEAEs with fatal outcome. In addition, a separate summary of death events including on treatment and post treatment deaths will be provided if appropriate.

All the deaths in the clinical database will be listed.

2.7.3 Laboratory data

For all safety analysis based on laboratory data, the information obtained from the central as well as local labs will be used. For summaries by visits, local lab data will be used when the corresponding central lab data are missing. For summaries on overall post-baseline data, all available data (including central and local lab data) from scheduled and unscheduled visits will be used.

Laboratory evaluations' summaries will be presented for groups of laboratory data (clinical chemistry, clinical hematology, urinalysis, UACR, coagulation/markers of thrombosis and reproductive and thyroid hormone panel).

For all continuous laboratory parameters, the absolute on-treatment laboratory values will be summarized with standard descriptive statistics (mean, median, standard deviation, minimum, maximum) by parameter, and scheduled visit/time-point. The on-treatment laboratory values will be defined as in [Section 2.7](#).

For categorical laboratory parameters and categorical urinalysis parameters, a frequency table of results will be produced by laboratory parameter, scheduled visit and time-point.

It is to be noted that for analysis on SAF, different baseline values need to be considered as mentioned in [Section 2.1.1.2](#).

For summary tables on laboratory parameters considering values, which are lower or greater than the limit of quantification:

- The values less than Lower Limit of Quantification (LLoQ) will be imputed to $0.5 \times \text{LLoQ}$ and the values greater than Upper Limit of Quantification (ULoQ) will be imputed to $1.5 \times \text{ULoQ}$.
- The number and percentage of values below the LLoQ and above the ULoQ will be presented.

For the figures, imputed values will be displayed.

Plots of arithmetic mean (SD) for all lab values will be provided. Note that displays of reproductive hormone level parameters (Testosterone, DHT, LH, FSH) will be further split by sex.

The lab abnormalities using the CTCAE grading will be reported. The version 4.03 of the CTCAE grading will be used at the time of reporting and the following reports will be provided:

- New or worsening abnormalities based on CTCAE grade (hematology, chemistry)
- Shift tables based on CTCAE grade (hematology, chemistry).

For selected laboratory parameters, abnormalities occurring at any time-point from scheduled, unscheduled and premature discontinuation visits considering all post-baseline on-treatment data will be summarized. Where normal ranges are available, abnormalities in laboratory data will be listed by participant and visit/time.

Liver toxicities

A criterion-based table for selected liver function tests and AEs will be presented including the number and percentage of the events described in [Table 2-2](#). In the PNH indication, aspartate aminotransferase (AST) can increase for reasons not related to liver toxicity and therefore should not be considered in the derivation of liver toxicities. Moreover INR is routinely monitored and can be used for the definition of liver function events. Events for the PNH indication are described in [Table 2-2](#).

Liver toxicity finding based on laboratory values and accounting for presence of bone pathology, symptoms, Gilbert syndrome will be presented. AEs collected in the analysis dataset and related

to liver toxicities (Jaundice, AE potentially indicative of a liver toxicity) will either be reported separately in a specific table or will simply be displayed as part of the general AE tables.

Table 2-2 Liver Toxicities

Definition	Label for output display
Potential Hy's Law case	
(ALT or AST > 3 × ULN) and TBL > 2 × ULN and ALP to ≤ 2 × ULN in the absence of bone pathology ^a (ALT or AST > 3 × ULN) and TBL > 2 × ULN and ALP to ≤ 3 × ULN in the presence of bone pathology ^a	Potential Hy's Law case
ALT elevations	
If ALT ≤ ULN at baseline: (ALT > 3 × ULN) and INR > 1.5 If ALT > ULN at baseline then criteria for ALT are defined as ALT > 2 x baseline or > 300 U/L and INR > 1.5	(ALT > 3 × ULN) and INR > 1.5
ALT > 8 × ULN	ALT > 8 × ULN
If ALT ≤ ULN at baseline: ALT > 5 to ≤ 8 × ULN If ALT > ULN at baseline then criteria for ALT are defined as ALT > 3 x baseline or > 300 U/L	ALT > 5 to ≤ 8 × ULN
If ALT ≤ ULN at baseline: ALT > 3 to ≤ 5 × ULN (accompanied by symptoms) ^a If ALT > ULN at baseline then criteria for ALT are defined as ALT > 2 x baseline or > 300 U/L (accompanied by symptoms) ^a	ALT > 3 to ≤ 5 × ULN with symptoms
If ALT ≤ ULN at baseline: ALT > 3 to ≤ 5 × ULN (patient is asymptomatic) ^a If ALT > ULN at baseline then criteria for ALT are defined as ALT > 2 x baseline or > 300 U/L (patient is asymptomatic) ^a	ALT > 3 to ≤ 5 × ULN no symptoms
ALP (isolated)	
ALP > 2 × ULN (in the absence of known bone pathology) ^a ALP >3 x ULN (if bone pathology ^a is present)	ALP > 2 × ULN (>3 x ULN if bone pathology is present)
TBL: total bilirubin ALT: alanine aminotransferase ^a concomitance between abnormal laboratory values and symptoms or disease (bone disease, Gilbert syndrome) will be established based on reported AEs or medical history with a start date prior to laboratory measurement and stop date posterior to laboratory measurement. Selection of AEs and medical History is described in Table 2-3 and provided in eCRS ^b Selection of AEs described in Table 2-3 and provided in eCRS	

When a criterion contains multiple laboratory parameters (e.g. ALT or AST > 3 × ULN), the criterion should be considered as met only if the elevation in parameters occurs on the same sample day (as evidenced by the same date that the lab samples were taken).

Table 2-3 Definition of symptoms and AEs for liver toxicities

Term in table	MedDRA term(s)
Bone pathology	HLGT = Bone disorders (excl congenital and fractures)
Symptoms:	
Severe Fatigue ⁽¹⁾	PT = Fatigue
Abdominal pain right upper quadrant	PT = Abdominal pain upper
Nausea	PT = Nausea
Vomiting	PT = Vomiting
General malaise	PT = Malaise
Rash with eosinophilia	PT = Drug reaction with eosinophilia and systemic symptoms
Gilbert syndrome	PT = Gilbert's syndrome
Jaundice	PT = Jaundice PT = Jaundice cholestatic
AEs indicative of liver toxicity	
Hepatic failure	HLT = Hepatic failure and associated disorders
Hepatic fibrosis and cirrhosis	HLT = Hepatic fibrosis and cirrhosis PT = Hepatic cirrhosis
Non-infectious hepatitis	PT = Hepatitis PT = Hepatitis acute PT = Hepatitis toxic PT = Hepatitis fulminant PT = Hepatitis chronic active PT = Hepatitis chronic persistent
Liver neoplasm	HLGT = Hepatobiliary neoplasms

HLT: High Level Term

HLGT: High Level Group Term

MedDRA codes listed above are based on version 23.1 The list will be updated for each MedDRA version change and will be included in the eCRS. eCRS will be the reference for analyses.

(1) presence of Fatigue term with severity ≥ "Severe"

Renal alert values will be summarized where renal alert values are identified as:

- Serum creatinine increase ≥ 25% compared to baseline during normal hydration status
- New onset dipstick proteinuria ≥ 3+

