5.2 Exclusion criteria

Participants meeting any of the following criteria are not eligible for inclusion in this study.

1. Participation in any other investigational drug trial or use of other investigational drugs at the time of enrollment, or within 5 elimination half-lives of enrollment, or within 30 days of enrollment, whichever is longer; or longer if required by local regulations.
2. Prior treatment with a complement inhibitor, including anti-C5 antibody.
3. History of hypersensitivity to iptacopan or any of its excipients or to drugs of similar chemical classes.
4. Known or suspected hereditary complement deficiency.
5. History of hematopoietic stem cell transplantation.
6. Patients with laboratory evidence of bone marrow failure (reticulocytes $<100 \times 10^9/L$, platelets $<30 \times 10^9/L$, neutrophils $<0.5 \times 10^9/L$).
7. Active systemic bacterial, viral (incl. COVID-19) or fungal infection within 14 days prior to study drug administration.
8. Presence of fever ≥ 38 °C (100.4 °F) within 7 days prior to study drug administration.
9. Human immunodeficiency virus (HIV) infection (known history of HIV or test positive for HIV antibody at Screening).
10. History of recurrent invasive infections caused by encapsulated organisms, e.g. meningococcus or pneumococcus.

11. Major concurrent comorbidities including but not limited to: severe kidney disease (e.g., eGFR<30 mL/min/1.73m², dialysis), advanced cardiac disease (e.g., NYHA class IV heart failure), severe pulmonary disease (e.g., severe pulmonary hypertension (WHO class IV)), or hepatic disease (e.g., active hepatitis) that in the opinion of the investigator precludes participant's participation in the study.
12. Liver disease, such as active hepatitis B virus (HBV) or hepatitis C virus (HCV) infection defined as HBsAg positive or HCV RNA positive, or liver injury as indicated by abnormal liver function tests at Screening:
 - Any single parameter of alanine aminotransferase (ALT), gamma-glutamyl transferase (GGT), alkaline phosphatase must not exceed 3 × ULN.
13. Unstable medical condition including, but not limited to, myocardial ischemia, active gastrointestinal bleeding, coexisting chronic anemia unrelated to PNH, or unstable thrombotic event not amenable to active treatment as judged by the investigator at Screening.

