8.3.3 Breakthrough hemolysis

The occurrence of BTH will be monitored continuously during the Core treatment period.

The criteria for clinical breakthrough is defined in [Table 8-3](#) below if either one of the two clinical criteria is met, in presence of the laboratory evidence of intravascular hemolysis and should be reported in the 'Breakthrough hemolysis' CRF page in addition to the AE page.

In contrast to clinical breakthrough as defined, the isolated laboratory evidence of increased intravascular hemolysis, without meaningful decrease in hemoglobin and without other clinical signs or symptoms of hemolysis (per [Table 8-3](#)) is defined as subclinical breakthrough hemolysis, and should **not** be reported in the 'Breakthrough hemolysis' CRF page.

Table 8-3 Breakthrough hemolysis definition

	Clinical criteria		Laboratory criteria
	Hemoglobin levels	Signs or symptoms	LDH level
Clinical breakthrough*	Decrease equal to or more than 2 g/dL (compared to the latest assessment, or within 15 days)	Gross hemoglobinuria, painful crisis, dysphagia or any other significant clinical PNH-related signs & symptoms	> 1.5-times ULN and increased as compared to the last 2 assessments
Subclinical breakthrough	Decrease less than 2 g/dL (compared to the latest assessment, or within 15 days)	No clinical signs or symptoms, except moderate hemoglobinuria	> 1.5-times ULN and increased as compared to the last 2 assessments

LDH: lactate dehydrogenase; ULN: Upper Limit of Normal;

*The breakthrough is defined clinical if either one of the two clinical criteria is demonstrated, in presence of laboratory evidence of intravascular hemolysis (LDH level)

During the Extension treatment period, breakthrough hemolysis will be monitored continuously until the end of study visit following the same criteria and guidance described above.

The assessment could be based on local laboratory results. However, the investigator should also collect at the same time a sample for the central laboratory assessment of hemoglobin and LDH, whenever possible.

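### SAP 2.7.3 rules AST out of liver-toxicity derivation in PNH, but the potential Hy's Law row of Table 2-2 counts cases on AST, with no stated exception

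*SAP*

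**What the plan says.** Under the liver toxicities heading of SAP Section 2.7.3, a criterion-based table of liver tests and events is planned, reporting numbers and percentages. The text gives a PNH-specific rule: "aspartate aminotransferase (AST) can increase for reasons not related to liver toxicity and therefore should not be considered in the derivation of liver toxicities". Soon after comes "Events for the PNH indication are described in" Table 2-2, so the rule and the table are presented as belonging together.

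The first row of Table 2-2, potential Hy's Law case, has two lines. Without bone pathology the criterion is "ALT or AST > 3 × ULN) and TBL > 2 × ULN and ALP to ≤ 2 × ULN". With bone pathology it is the same except that the ALP limit becomes 3 × ULN. AST is an alternative to ALT in both.

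Below Table 2-2, the SAP requires elevations that form one criterion to fall on the same sample date. That rule opens "When a criterion contains multiple laboratory parameters (e.g. ALT or AST > 3 × ULN", which repeats the AST term.

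On data scope, the SAP says that for selected parameters "abnormalities occurring at any time-point from scheduled, unscheduled and premature discontinuation visits considering all post-baseline on-treatment data will be summarized". For overall post-baseline summaries, "all available data (including central and local lab data) from scheduled and unscheduled visits will be used".

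**The concern.** The rule and the row cannot both be applied. A programmer who follows the sentence derives the row from ALT alone; one who follows the table accepts either enzyme. The SAP does not say which prevails, so the same data can give two potential Hy's Law counts.

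This row is the most closely read line of a liver-safety display, and the trial is single-arm, so there is no concurrent control count to set it against. Under the table as written, a case that qualified only through AST appears under the same label as one that qualified through ALT. The reader of the table cannot separate the signal the SAP says to set aside from the one it means to report.

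**Working it through.** The documents give no figure to reproduce. The check sets the texts side by side and applies them to the same data.

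**Inputs**

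- AST rule: SAP 2.7.3, paragraph before Table 2-2. AST is not used.
- Hy's Law row: SAP Table 2-2. ALT or AST above 3 × ULN, with total bilirubin (TBL) above 2 × ULN, and ALP at or below 2 × ULN (3 × ULN with bone pathology).
- Same-day rule: SAP 2.7.3, after Table 2-2.
- Sample size: about 40 participants (Protocol 12.8.1, SAP Section 3).

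**Step 1. Is there an exemption?** None is stated. The five ALT rows of Table 2-2 use ALT and never AST, as the rule requires. The isolated ALP row is not informative, since it would not contain AST in any case. The conflict is confined to the Hy's Law row and the same-day example.

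**Step 2. Where do the two readings differ?** Take a single sample date with TBL above 2 × ULN and ALP within its limit:

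| ALT > 3 × ULN | AST > 3 × ULN | Table as written | AST rule applied |
|---|---|---|---|
| yes | yes | case | case |
| yes | no | case | case |
| no | yes | **case** | **not a case** |
| no | no | not a case | not a case |

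Only the third pattern differs. An assumed example is ALT 1 × ULN, AST 4 × ULN, TBL 2.5 × ULN, ALP 1 × ULN, no bone pathology. The table counts it because 4 > 3, 2.5 > 2 and 1 ≤ 2. With AST removed it is not counted, because ALT 1 ≤ 3.

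**Step 3. The same-day example.** The example is an either/or term. One enzyme satisfies it, so it does not illustrate concurrence. The pairing that has to be concurrent is the transaminase with bilirubin.

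**Step 4. Size per case.** One participant is 1/40 = 2.5%; two are 2/40 = 5.0%. The documents give no rate for raised AST or bilirubin, so the expected number of such participants cannot be calculated.

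**Step 5. Opportunity.** ALP is in the full chemistry panel but not the abbreviated one (Protocol Table 8-5). In the Core period the full panel after Day 1 falls on Days 56, 112 and 168, which is 3 of 11 scheduled visits (Protocol Table 8-1). This is not a firm ceiling. Unscheduled and local samples also count, Extension data enter up to the data cut-off, and the SAP does not say how a missing ALP is handled.

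**The case against.** The strongest defence is that the row is deliberate. Protocol Table 16-1 has the same structure, with ALT or AST for potential Hy's Law and ALT alone for the other transaminase triggers, and SAP Table 2-2 mirrors it. On that view the table is the operative text and the AST sentence merely explains why there are no stand-alone AST rows. A potential Hy's Law flag is also a screening device, so over-counting errs on the cautious side. Individual cases remain open to judgement through the participant listings and the causality work-up that the protocol requires.

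Much of this stands. The row may well be intended, the protocol trigger is not at fault, and simply deleting AST from the row would be debatable. But the SAP does not state the exception. Its rule is worded without limit and is tied to this table. Listings help with a single case; they do not settle which number goes into the row.

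Three stronger readings are tempting and are not supported:

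- *An isolated AST rise would be counted.* It would not. The row also needs bilirubin above 2 × ULN on the same day and ALP within its limit.
- *Hemolysis will produce false cases.* The protocol says "The occurrence of BTH will be monitored continuously during the Core treatment period", and exclusion criterion 12 limits only certain liver tests at Screening: "Any single parameter of alanine aminotransferase (ALT), gamma-glutamyl transferase (GGT), alkaline phosphatase must not exceed 3 × ULN". AST and bilirubin are absent from that list, and the Hy's Law row has no baseline condition. But the SAP does not name hemolysis as the source of the AST rise, and neither document says that hemolysis would take AST above 3 × ULN or bilirubin above 2 × ULN. These are assumptions.
- *The precision of a planned safety estimate is distorted.* Table 2-2 is planned as numbers and percentages, with no confidence interval.

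**Conclusion.** Wrong as written: an internal contradiction between the AST rule in SAP 2.7.3 and the potential Hy's Law row of Table 2-2, repeated in the same-day example. Severity is minor.

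The contradiction rests on the text alone and needs no clinical assumption. Its practical effect depends on how many participants show the one discordant pattern, and that is unknown and may be zero. The 2.5-point figure assumes a denominator of exactly 40. The effect is confined to one descriptive safety table. The primary and secondary analyses, the 15% threshold and the protocol's clinical actions for liver events are untouched.

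**What to change.** In SAP Table 2-2, split the potential Hy's Law row into two lines, each with the present TBL, ALP and bone-pathology conditions:

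1. *Criterion met through ALT > 3 × ULN*. This is the liver-toxicity count, in line with the AST rule.
2. *Criterion met through AST > 3 × ULN only (ALT ≤ 3 × ULN)*. State that this line is kept so that the table reconciles with Protocol Table 16-1.

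Assign a participant who meets both lines on different dates to line 1. The two lines then add up to the count under the row as it stands, and no protocol-trigger case disappears from view.

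Replace the same-day example with a true multi-parameter one: ALT > 3 × ULN and TBL > 2 × ULN.

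A sentence declaring Hy's Law an exception to the AST rule would also remove the contradiction, but it would leave the AST-only cases unmarked in the count. A flag for participants already meeting a line at baseline, or extra columns such as bilirubin fractions and LDH, would be optional.

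The cost is one extra table line and one reworded example. AST, ALT and total bilirubin are in both chemistry panels and ALP is in the full panel, so no new data are needed.

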2.1.1.2 Baseline definition

For the analysis on efficacy and safety data in the core treatment period on the analysis sets FAS and SAF as defined in [Section 2.2](#), the baseline value is defined to be the last result obtained at or prior to start of study treatment (Day 1) for baseline demographics, medical history, lab values, vital signs and ECGs. Most variables will have their baseline at Day 1, unless otherwise specified. For assessments not performed at Day 1, the assessment at the screening visit or most recent assessment prior to start of study treatment will be used as baseline. For baseline derivation of laboratory parameters, central lab measurements will be used. If there are no central lab data available, then local lab measurements will be used for baseline computations only.

- The baseline hemoglobin will be the mean of the two confirmatory measurements (planned) taken during screening that confirm the hemoglobin entry criterion in patients who do not receive a transfusion between the first and second confirmatory measurement. In patients who receive a transfusion after the first confirmatory measurement, the baseline will be the first measurement.

If there is only one confirmatory measurement but additional unplanned measurements taken during screening, for patients who do not receive transfusion in the screening, then the mean of the first measurement and the second measurement taken within 2 to 8 weeks after the first measurement will be considered to be the baseline. In patients who receive a transfusion after the first measurement, the baseline will be the first measurement. For patients with transfusion on same day, but hemoglobin measurement taken before transfusion, the baseline hemoglobin should be the average of the measurements considering the hemoglobin measurement before transfusion.

- The baseline score of fatigue using the FACIT-Fatigue questionnaire will be defined as the mean of first assessment prior to Day 1 and the Day 1 value. [REDACTED]
- The baseline LDH will be defined as the value on Day 1 (prior to starting treatment). If Day 1 value is not available, then the mean of two screening/LDH confirmatory values will be used. If screening value is not available, the baseline LDH will be defined as single confirmatory LDH value.

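### Without bone pathology, the isolated-ALP row of SAP Table 2-2 counts a stable ALP of > 2 to 3 × ULN that the protocol permits at Screening

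*SAP*

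**What the plan says.** SAP 2.7.3 plans a liver table on these terms: "A criterion-based table for selected liver function tests and AEs will be presented including the number and percentage of the events described in" Table 2-2. The unit of the count is not stated; counting each participant once is the natural reading. The isolated-ALP row is met by "ALP > 2 × ULN (in the absence of known bone pathology", or by ALP above 3 × ULN if bone pathology is present. Neither part refers to baseline.

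The data window is set in SAP 2.7: "Safety summaries (tables, figures) include only data from the on-treatment period with the exception of baseline data". SAP 2.7.3 does not limit Table 2-2 to new or worsened values.

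The ALT rows are built differently. For the > 5 to ≤ 8 × ULN row, for example: "If ALT > ULN at baseline then criteria for ALT are defined as ALT > 3 x baseline or > 300 U/L". Four of the five ALT rows have a clause of this kind; the exception is ALT > 8 × ULN.

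On entry, Protocol 5.2, exclusion criterion 12, says: "Any single parameter of alanine aminotransferase (ALT), gamma-glutamyl transferase (GGT), alkaline phosphatase must not exceed 3 × ULN". Protocol Table 16-1, which tells sites when to act, has the same isolated-ALP thresholds as the SAP row, also without a baseline clause.

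**The concern.** The protocol admits a range of ALP values that the SAP then reports in a table of liver toxicities. A participant whose ALP lies in that range at entry and never moves will meet the row at the first on-treatment ALP measurement. The row total therefore mixes two kinds of participant: those who crossed the threshold on iptacopan, and those who were above it before the first dose.

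The study has one arm, so no control column shows how often such a value is pre-existing. A reader who sees a non-zero count cannot tell from the row which kind it contains. Elsewhere in the same part of the SAP, baseline is taken into account: the ALT rows have their alternative rule, the renal alerts use a rise in creatinine from baseline and new-onset proteinuria, and the ECG limits add changes from baseline to absolute values.

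**Working it through.** The documents give no figure to reproduce. The check is a comparison of thresholds.

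**Inputs**
- ALP permitted at Screening: ≤ 3 × ULN (Protocol 5.2, criterion 12).
- ALP counted on treatment: > 2 × ULN without bone pathology, > 3 × ULN with it (SAP Table 2-2).
- Planned size: about 40 participants (Protocol 3; SAP 1.1).
- ALP sampling: full chemistry panel only (Protocol Table 8-5), scheduled at Screening, Days 1, 56, 112 and 168 in Core, and Days 224 and 336 in the Extension (Protocol Tables 8-1 and 8-2).

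**Overlap of permitted and counted values**
- Without bone pathology: (≤ 3) and (> 2) overlap on > 2 to 3 × ULN. An unchanged value of, say, 2.5 × ULN is permitted and counted.
- With bone pathology: (≤ 3) and (> 3) do not overlap. No unchanged permitted Screening value is counted.

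**The same test on the ALT rows**
- ALT is also capped at 3 × ULN at Screening, and every ALT row starts above 3 × ULN under its ULN-based rule. An unchanged permitted ALT does not meet that rule.
- Under the baseline-relative rule, an unchanged value cannot exceed two or three times itself. The fixed 300 U/L alternative could be met by a permitted value only if the laboratory's ULN for ALT were above 300/3 = 100 U/L; the documents do not give the ULN.
- So the overlap is a feature of the ALP row.

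**Size**
- Let k be the number of participants without bone pathology who have a stable ALP of > 2 to 3 × ULN. The documents do not give k.
- Contribution to the row, counting participants: k/40. For assumed k = 0, 1, 2 this is 0%, 2.5% and 5.0%.

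**Would an ALT-style rule be the right repair?**
- If the row required a multiple of a raised baseline, a participant at 2.5 × ULN would be counted only above 1.5 × 2.5 = 3.75, 2 × 2.5 = 5.0 or 3 × 2.5 = 7.5 × ULN, for assumed multiples of 1.5, 2 and 3.
- Each removes the unchanged value, but each also hides real rises below the new limit, and the documents give no basis for choosing the multiple for ALP. Splitting the existing count avoids that choice.

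**The case against.** The strongest reply is that the row is faithful to the protocol. It repeats the isolated-ALP criterion of Protocol Table 16-1, which has baseline alternatives for ALT and none for ALP, so the SAP simply reports how often a protocol criterion was met. That stands as far as it goes: the row does not depart from the protocol. But Table 16-1 tells sites when to retest and look for a cause, where a low threshold protects the participant. A table of counts and percentages serves another purpose, and copying the trigger does not make the count treatment-emergent.

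Second, other outputs give the missing context. SAP 2.7.3 plans new-or-worsening and shift tables by CTCAE grade, and a listing of laboratory abnormalities by participant and visit where normal ranges exist. With about 40 participants, an affected person can be traced. This also stands and limits the consequence, but none of those outputs separates the two groups in the row itself.

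Third, a reader might infer that the SAP attributes a stable ALP to iptacopan. It does not. The label for output display is the plain threshold, and Liver Toxicities is the SAP's table heading.

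A reader might also infer that the Potential Hy's Law row has the same gap in the opposite direction, because it requires "TBL > 2 × ULN and ALP to ≤ 2 × ULN in the absence of bone pathology". The documents do not support that. A ceiling on ALP is a deliberate part of that definition in both Protocol Table 16-1 and SAP Table 2-2. If such a participant's baseline ALT is normal, any ALT above 3 × ULN still falls in one of the ALT rows, and the ALP value still appears in the ALP row.

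**Conclusion.** The point holds for participants without bone pathology and is minor. A stable ALP of > 2 to 3 × ULN, permitted at Screening, is counted in the isolated-ALP row. Extending this to participants with bone pathology would be wrong, because their cut-off equals the Screening cap.

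It would also be wrong to infer that the safety conclusions in general are affected. The treatment-emergent AE tables, the CTCAE outputs and the primary endpoint do not use this row. The effect is on one descriptive count, at 2.5 percentage points per affected participant. That size assumes about 40 participants in the Safety Set, each counted once. The number affected is unknown and may be zero.

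**What to change.** Change the SAP only.

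1. Keep the criterion (> 2 × ULN, or > 3 × ULN with bone pathology) and the row total, and state that the row counts participants.
2. Under the total, split by baseline ALP: ≤ 2 versus > 2 × ULN, or ≤ 3 versus > 3 × ULN with bone pathology. The lower group shows how many crossed the threshold newly on treatment. Use the definition already in SAP 2.1.1.2: "the baseline value is defined to be the last result obtained at or prior to start of study treatment (Day 1"). This is normally the Day 1 value, so the split also covers someone whose ALP rose above the Screening cap before dosing.
3. For participants with a raised baseline, give baseline ALP, highest on-treatment ALP and their ratio, for example as extra columns in the abnormality listing already planned in SAP 2.7.3. Do not label every increase above baseline as worsened: the highest of several values can exceed a single baseline value through measurement variation alone.
4. Leave the Table 16-1 site trigger and the Hy's Law definition unchanged. Raising the trigger would weaken monitoring.

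The cost is one split and a few listing columns in the liver-table program. No protocol amendment or new sample is needed, because ALP is already measured at Screening and Day 1. The downside is a slightly longer table.
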